8.2.6 Quality Assurance for radiotherapy

For quality assurance purposes in the EXCITE trial, a Radiotherapy Plan Assessment form will be collected for each patient on the trial. The form will collect data on the dose given (planned and actual), the different volumes (GTV, CTV & PTV), treatment fields, target coverage, dose volume constraints and other treatment details and interruptions. Each form will be sent directly to the Research Superintendent Radiographer at Glan Clwyd Hospital, using the following email address [contact].

8.3 Ionising Radiation (Medical Exposure) Regulations (IRMER)

Taking account of potential variations in practice at other sites, there are no additional radiation exposures within this trial (radiotherapy and CT scanning during the planning of radiotherapy) when compared to standard practice, and to comply with the above regulations, the radiation exposures will be approved by the Main REC.

Trials to be undertaken on multiple sites have to meet all the applicable requirements of IRMER at each site, therefore each PI needs to comply with their employer's policies and procedures for the use of ionising radiation in research prior to recruitment.

8.4 Modification of trial treatment

Dose modifications should be made according to the worst grade of adverse event (NCI CTC v3.0).

8.4.1 Capecitabine: General principles of dose modification

Toxicity due to capecitabine administration may be managed by symptomatic treatment and/or modification of the dose (treatment interruption or dose reduction). Once the dose has been reduced, it should not be increased at a later time. Patients should be informed of the need to interrupt treatment immediately if moderate (grade 2) or severe (grade 3 or 4) toxicity occurs.

In the case of capecitabine doses being omitted because of toxicity or other reasons (such as patient forgetfulness) or if a dose of capecitabine is compromised because a patient vomits following an oral dose, then no attempt should be made to add extra doses of capecitabine to account for this and instead treatment should simply resume at the next due dose.

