Capecitabine side effects: The side effect profile of capecitabine is similar to 5FU. The main toxicities are hand-foot syndrome, diarrhoea, nausea and stomatitis. Vomiting, fatigue, abdominal pain, dermatitis, fever, parasthesia, headache, dizziness, insomnia, anorexia and a drop in white blood cells are also experienced.

Occasionally, the following problems have been reported: taste disturbance, chest pain, angina pectoris, abnormal drowsiness or lethargy, weakness, dehydration and alopecia.

Capecitabine is contraindicated in patients with moderate or severe renal impairment. Antacids containing aluminium hydroxide may interfere with the absorption of capecitabine and so an alternative should be prescribed if possible.

Capecitabine precautions: Altered coagulation and/or bleeding have been reported in patients taking coumarin-derivative anticoagulants concomitantly with capecitabine. These events occurred within several days and up to several months after initiating capecitabine and also within one month of stopping capecitabine. Patients should be monitored regularly (twice weekly during CRT) for alterations in their coagulation parameters.

Phenytoin plasma concentrations have been shown to increase when used concomitantly with capecitabine. Again, patients should be regularly monitored for increase in phenytoin plasma concentrations and associated clinical symptoms.

Capecitabine should not be administered together with sorivudine [an antiviral] or its chemically related analogues such as brivudine. A chemically significant drug-drug interaction between sorivudine and 5FU, resulting from the inhibition of dihydropyrimidine dehydrogenase [DPD] by sorivudine has been described in literature. This interaction is potentially fatal as it leads to increased fluoropyrimidine toxicity.

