It has been the experience of the Trial Management Group (TMG) in the NWCOG-2 trial that despite warnings of potential side effects, there sometimes remains in the patient's mind, the perception that because capecitabine is a tablet, it does not have the same potential to cause side effects as intravenous chemotherapy. It has to be emphasised to patients that oral chemotherapy has the same potential to cause side effects as intravenous chemotherapide to cause side effects as intravenous chemotherapy. It has to be emphasised to patients that oral chemotherapy has the same potential to cause side effects as intravenous chemotherapy and if rapidly worsening side effects are occurring, that they must stop the capecitabine tablets immediately and ring in to contact numbers for medical advice.

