8.4.7 Irinotecan: General principles of dose modification

Irinotecan dose reductions are permanent

Toxicity grade	Diarrhoea	Radiothera py	Cetuximab	Capecitabine	Irinotecan
1	increase of <4 stools per day over pretreatment level	Continue	100%	100%	Continue
2	increase of 4-6 stools per day over pretreatment levels or moderate cramping	Continue	100%	100%*	Interrupt until grade 0-1; then 100%
3**	increase of 7-9 stools/day or incontinence (if patient continent prior to treatment), severe cramping	Interrupt until grade 0-1	100%	Interrupt until grade 0-1; then 75%	Interrupt until grade 0-1; then 75%
4	increase of => 10 stools per day, grossly bloody diarrhoea, need for parenteral support haemorrhagic dehydration	Interrupt until grade 0-1	Discontinue	Discontinue	Discontinue

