8.4.8 Dose modification and treatment for acute gastrointestinal toxicity

*If no response to loperamide, reduce capecitabine dose to 75%

** if grade 3, lasts more than 24 hours and delays radiotherapy, stop chemotherapy until recovery

Figure 7: Dose modification for acute GI toxicity.

For grade 1 and 2 diarrhoea, loperamide (2 mg as required up to 8 times per day) can give symptomatic relief.

Radiation treatment will be interrupted when grade 3 or 4 toxicity occurs. Treatment can then be re-commenced after recovery from toxicity. However it is important that recovery to either grade 0 or 1 occurs prior to restarting therapy.

In the event of severe toxicity (grade 3 or 4 diarrhoea), the patient should receive full supportive care. It is recommended that such patients should be admitted to hospital and treated with intravenous fluids, loperamide and antibiotics, especially when there is concomitant grade 3 or 4 neutropenia. In the presence of rapidly falling serum albumin, total parenteral nutrition should be added. If \geq grade 3 gastrointestinal toxicity occurs in the presence of \geq grade 3 neutropenia then GCSF at 30 MU subcutaneously (or equivalent according to local practice) should be added for five days or until recovery to \leq grade 2 neutropenia.

Some patients receiving CRT will experience diarrhoea which may initially present as grade 3 but become controlled by loperamide within a few hours and can then be managed in routine clinical practice as the recommendations above for grade 2 diarrhoea.

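### Section 8.4.1 has patients told to interrupt capecitabine at any grade 2 toxicity, while Figure 7 continues it without a break in grade 2 diarrhoea, and nothing says which text prevails

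*Protocol*

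**What the plan says.** Section 8.4.1 sets out general principles for capecitabine. It opens by allowing more than one response: "Toxicity due to capecitabine administration may be managed by symptomatic treatment and/or modification of the dose (treatment interruption or dose reduction"). It then gives an instruction for patients: "Patients should be informed of the need to interrupt treatment immediately if moderate (grade 2) or severe (grade 3 or 4) toxicity occurs". No toxicity is excepted and no later table is referred to. Section 8.2.2 places diarrhoea within scope: "The main toxicities are hand-foot syndrome, diarrhoea, nausea and stomatitis".

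Figure 7, printed with sections 8.4.7 and 8.4.8, sets doses for acute gastrointestinal toxicity. Grade 2 is defined as "increase of 4-6 stools per day over pretreatment levels or moderate cramping". In that row radiotherapy continues, cetuximab is 100%, and capecitabine is 100% with an asterisk. The irinotecan cell reads "Interrupt until grade 0-1; then 100" per cent. The asterisk leads to: "If no response to loperamide, reduce capecitabine dose to 75" per cent. The text below the table adds: "For grade 1 and 2 diarrhoea, loperamide (2 mg as required up to 8 times per day) can give symptomatic relief". It does not mention a capecitabine break at grade 2.

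Section 8.2.2 also has patients told that "if rapidly worsening side effects are occurring, that they must stop the capecitabine tablets immediately", and that they should telephone for medical advice.

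**The concern.** Two parts of the current protocol give different answers to one question: what happens to capecitabine when a patient has grade 2 diarrhoea? Under section 8.4.1 the patient has been told to stop at once. Under Figure 7 the drug carries on, at full dose or at 75%.

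This matters more for capecitabine than for the infused drugs. It is taken at home twice a day, so what the patient has been told largely decides what is swallowed before a clinician is involved. Section 8.2.2 records that patients in the predecessor trial tended to underestimate the tablets, which is a reason for unambiguous wording. Diarrhoea is also the toxicity that section 13 describes as the most common serious one with irinotecan-containing chemoradiotherapy.

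The two routes can also part for the rest of the course. Section 8.4.1 makes capecitabine reductions permanent, so a patient who continues under Figure 7 and does not respond to loperamide stays at 75%, whereas section 8.4.1 would have begun with an interruption.

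**Working it through.** The protocol states no figure on this point, so the check is a comparison of texts.

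**Capecitabine at grade 2, source by source**

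- Section 8.4.1, what patients are told: interrupt immediately.
- Figure 4, hand-foot syndrome: interrupt until grade 1 or less, then restart at a percentage that depends on the number of episodes.
- Figure 9, other non-haematological toxicity: interrupt until grade 0 or 1, then 100%.
- Figure 7, diarrhoea: 100%, or 75% if loperamide fails; no interruption.
- Figure 10, haematological toxicity: 100%; no interruption.

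**Is diarrhoea within section 8.4.1?** Yes. That section concerns toxicity due to capecitabine, and section 8.2.2 names diarrhoea among the drug's main toxicities.

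**Could 100% in Figure 7 be the dose on restarting after a break?** No. The irinotecan cell in the same row and the capecitabine cell in the grade 3 row both write out an interruption followed by a percentage. Where the table intends a break it says so, so a bare 100% means continue. The footnote is a reduction, which is not a break either.

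**Does any text rank the two?** No. Section 8.4.10 says that Figure 9 covers effects not dealt with in earlier sections, which settles Figure 9 against Figure 7. Nothing similar settles section 8.4.1 against Figure 7.

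**Is the conflict confined to events that begin at grade 2?** Not quite. Section 8.4.8 lets diarrhoea that first presents as grade 3 but is controlled by loperamide within a few hours be managed as grade 2. Figure 7 then keeps capecitabine at 100%, while section 8.4.1 has told that patient to interrupt.

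**What can be sized?** The schedule is 25 radiotherapy days with two doses a day: 25 × 2 = 50 planned doses. One day is 2/50 = 4% of the course. Going further needs the frequency and duration of grade 2 diarrhoea, and the protocol gives neither.

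**The case against.** The best defence is that the two texts speak to different people at different moments. Section 8.4.1 governs what the patient does at home before anyone has graded the event; Figure 7 is the clinician's dose table. A workable sequence exists: the patient holds the tablets, rings in, is graded, starts loperamide and is dosed by Figure 7. The advice in section 8.2.2 to stop and telephone fits this. One can add that section 8.4.1 is headed as general principles, that its opening allows symptomatic treatment, and that Figure 10 also keeps capecitabine at 100% at grade 2, so the sentence may never have been meant as an absolute dosing rule.

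Part of this stands. A reader might infer that the same patient is told both to stop and to continue. The protocol does not say so, because Figure 7 is nowhere given to patients; the conflict is between a patient instruction and a dose table. Nor is section 8.2.2 a competing third trigger, since stopping and ringing in when side effects deteriorate quickly contradicts neither text.

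The defence does not remove the inconsistency. Neither the hold-and-call sequence nor precedence of the specific table is written anywhere. Two of the specific tables, Figures 4 and 9, follow section 8.4.1 at grade 2, so a site has no signal that diarrhoea is a deliberate exception. Figure 10 concerns laboratory values that a patient would not notice, so it says little about how the patient instruction should be read.

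**Conclusion.** The inconsistency is real and lies in the current text. For grade 2 diarrhoea the instruction to patients and the dose table disagree on whether capecitabine is interrupted, and no passage settles it. Handling may therefore vary between sites and patients. This is a moderate, safety-relevant inconsistency of wording. It touches no endpoint definition, sample size or decision rule.

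Three stronger conclusions are tempting and are not supported.

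- *A large loss of dose.* If grade 2 diarrhoea lasted 3 to 10 treatment days (assumed), 3 × 4% = 12% to 10 × 4% = 40% of an affected patient's doses would depend on the rule followed. If 20% to 50% of patients were affected (assumed), the cohort mean would move by 0.20 × 12% = 2.4% to 0.50 × 40% = 20%. A reader might set the per-patient figures beside the 86% mean capecitabine delivery in section 2.5, a shortfall of 14 points. That is a cohort mean from a seven-day schedule, and much of the cohort range falls below 14. The upper end also ignores the footnote: at 75% dosing, 40% becomes 0.75 × 40% = 30%. Under hold-and-call, the gap is only the time to clinical contact. The range illustrates; it does not measure.
- *Distortion of the diarrhoea stopping count or the R0 rate.* Nothing in the protocol links capecitabine handling at grade 2 to either.
- *A protocol deviation whichever text is followed.* Section 8.4.1 itself provides for doses omitted because of toxicity, with treatment resuming at the next due dose.

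The conclusion rests only on the wording of section 8.4.1 and Figure 7, and on no assumed figure.

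**What to change.** Reconcile section 8.4.1 with the grade 2 diarrhoea row of Figure 7 and its footnote, so that one statement governs capecitabine in that event. The revised text should say how the patient instruction relates to the dose table: whether the table takes over once the event has been graded, whether diarrhoea is an exception to section 8.4.1, or whether the Figure 7 cell changes. It should also cover diarrhoea that presents as grade 3 and is then managed as grade 2 under section 8.4.8. Use matching wording in the advice given to patients, including section 8.2.2. Which clinical rule applies is for the sponsor's clinical team; this review takes no view.

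The cost is a short protocol amendment and matching patient wording, with no extra patients, procedures or analyses.

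### Section 8.4.1 has patients told to interrupt capecitabine at grade 2 toxicity, but Figure 7 continues it through grade 2 diarrhoea, and nothing says which prevails

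*Protocol*

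**What the plan says.** **General rule.** Section 8.4 opens with "Dose modifications should be made according to the worst grade of adverse event (NCI CTC v3.0"). Section 8.4.1, on capecitabine, says that toxicity "may be managed by symptomatic treatment and/or modification of the dose (treatment interruption or dose reduction"). It then says that patients are to be told to "interrupt treatment immediately if moderate (grade 2) or severe (grade 3 or 4) toxicity occurs". No type of toxicity is excepted. The same section says that a reduced dose is not raised again and that omitted doses are not replaced.

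**Diarrhoea table.** Figure 7 defines grade 2 as "increase of 4-6 stools per day over pretreatment levels or moderate cramping". In that row the capecitabine cell is 100% with an asterisk. The footnote to the asterisk reads "If no response to loperamide, reduce capecitabine dose to 75" per cent. The irinotecan cell in the same row has the drug interrupted until grade 0-1 and then given at 100%.

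**Grade 3 diarrhoea.** The Figure 7 row interrupts radiotherapy, capecitabine and irinotecan until grade 0-1, with both drugs then given at 75%. A second footnote says "if grade 3, lasts more than 24 hours and delays radiotherapy, stop chemotherapy until recovery". The last paragraph of section 8.4.8 says that some diarrhoea "may initially present as grade 3 but become controlled by loperamide within a few hours", and allows it to be managed as grade 2.

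**The concern.** Capecitabine is taken at home, twice a day, without a clinician present. What the patient has been told therefore decides what happens first, and the dose table comes into play only when the site is in contact. If the two differ, a patient with grade 2 diarrhoea may stop tablets that the table continues, or may be told by the site to go on after being told beforehand to stop. Practice could then differ between sites and between patients.

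The toxicity concerned is not a marginal one. Section 13 names diarrhoea as the most common serious toxicity of irinotecan-containing chemoradiation and monitors grade 3 or 4 diarrhoea with a view to early stopping. Any difference in capecitabine exposure would arise during the toxicity that the trial watches most closely.

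**Working it through.** No sample size, power or event count is involved, so there is no figure to reproduce. The check sets the passages side by side. Under section 8.4.1, "treatment" is taken to mean capecitabine, since that is the subject of the section.

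**Grade 2, capecitabine**

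| Place in protocol | Toxicity | Action on capecitabine |
|---|---|---|
| 8.4.1 | any | patient told to interrupt at once |
| Figure 7 | diarrhoea | 100%; 75% if loperamide fails; no interruption |
| Figure 4 | hand-foot syndrome | interrupt, then restart (100% after the first appearance) |
| Figure 9 | other non-haematological | interrupt until grade 0-1, then 100% |
| Figure 10 | white cells, neutrophils | 100% |

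1. Could the bare 100% in Figure 7 be shorthand for interrupting and then resuming at 100%? No. The irinotecan cell in the same row writes the interruption out, and so does the capecitabine cell at grade 3. The table states interruption where it means it.
2. Does the footnote restore agreement? No. It changes the dose from 100% to 75% and still does not interrupt.
3. Is there a rule of precedence? The lead-in to Figure 9 confines that table to side effects not covered in earlier sections. No sentence says that Figure 7 overrides 8.4.1, or the reverse.
4. Do the other tables settle it? No. Figures 4 and 9 agree with 8.4.1 at grade 2. Figure 10 departs from it for white cells and neutrophils, but those are laboratory values that a patient at home would not notice.
5. Section 8.2.2 adds a further trigger: patients are to stop tablets and ring in if side effects are worsening rapidly. That is neither the grade 2 trigger of 8.4.1 nor the loperamide test of Figure 7.

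**Grade 3 diarrhoea**

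1. Section 8.4.1 and the Figure 7 row agree: both interrupt capecitabine.
2. The second footnote stops chemotherapy when grade 3 lasts over 24 hours and delays radiotherapy. The row already interrupts capecitabine, irinotecan and radiotherapy at grade 3, so it is unclear what the footnote adds.
3. An episode that is briefly grade 3 falls under two descriptions. By worst grade (section 8.4), the grade 3 row applies: radiotherapy is interrupted, and capecitabine and irinotecan are interrupted and then given at 75%. By the last paragraph of 8.4.8, the grade 2 row applies: radiotherapy continues, capecitabine stays at 100% unless loperamide fails, and irinotecan is interrupted and then given at 100%.
4. The choice persists, because capecitabine is not increased after a reduction (8.4.1) and irinotecan reductions are permanent (8.4.7).

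**The case against.** The strongest defence is that the two passages do different jobs. Section 8.4.1 is headed as general principles and describes what patients are told; Figure 7 is the specific table for the treating team. The section also allows symptomatic treatment, which fits a loperamide-first approach. On this reading the patient holds the tablets, rings in, and the clinician then applies the table. That is plausible, and it makes the conflict less stark than two flatly opposed orders to the same person. But the protocol does not say it. The nearest support, in 8.2.2, concerns rapidly worsening effects rather than grade 2 as such. Even on this reading, tablets that Figure 7 continues would have been missed and not replaced.

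The defence succeeds on several stronger readings that a reader might infer:

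- **That grade 3 has an equal contradiction.** It does not. Section 8.4.1 and the table agree there. The second footnote does not say that chemotherapy stops only under its conditions. The short-episode paragraph is an express exception, and section 8.1 draws a comparable line when it makes grade 3 diarrhoea dose-limiting only if it fails to improve within 24 hours. What stands is the tension with the worst-grade sentence and the unclear role of the footnote.
- **That the early-stopping count becomes ambiguous.** Section 13 counts patients with grade 3 or 4 diarrhoea. Section 8.4.8 changes how a brief episode is managed, not how it is graded.
- **That capecitabine exposure cannot be interpreted.** Section 9.1.2 has compliance recorded weekly, so missed doses should be visible.

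**Conclusion.** The grade 2 rule for capecitabine is wrong as written: 8.4.1 has the patient interrupt, Figure 7 continues the drug in both of its branches, and the protocol does not rank them. This rests on the text alone, with the Figure 7 cells read as the extracted table shows them. The grade 3 point is a secondary ambiguity.

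The size cannot be given as a number of patients or a share of dose. The protocol states no grade 2 diarrhoea rate and no expected length of interruption. A reader might apply the 20% diarrhoea rate that section 13 reports from the earlier trial, but that is a grade 3 or 4 rate, from a regimen with capecitabine seven days a week and no cetuximab, so it does not measure a conflict at grade 2. Nor do the documents show any effect on the R0 resection rate or its test. The point matters for consistent conduct and for reading the toxicity data, and should be corrected on those grounds.

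**What to change.** The sponsor should reconcile section 8.4, section 8.4.1, Figure 7 with both footnotes, and the last paragraph of section 8.4.8, so that a single rule applies to capecitabine at each grade of diarrhoea. The text should state:

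- which passage governs where the general principle and a specific table differ;
- what the second footnote to Figure 7 adds to the grade 3 row;
- how the short-episode exception stands against the worst-grade sentence.

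The same rule should be carried into what patients are told, including the advice in 8.2.2. Which rule is adopted is for the sponsor and its clinicians. The cost is protocol wording and matching patient instructions; no new procedure or data item is needed.
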